3 OBJECTIVES AND PURPOSE

Objectives:

1: To demonstrate the effectiveness of a SSU AHF management strategy vs. usual AHF care (i.e. inpatient admission), using a randomized, controlled, simple, trial design.

2. To demonstrate that a SSU AHF strategy of care leads to equivalent or improved adherence to HF guidelines at time of discharge vs. usual care (i.e. hospitalization).

Purpose:

The overarching goal of this comparative effectiveness study is to increase days-alive-and-out-of-the-hospital (DAOOH) and improve quality of life (QoL) for lower risk AHF patients who present to the emergency department (ED). We hypothesize an alternative to hospitalization, SSU AHF management of less than 24 hours, will achieve our goal.

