7.3.7 SCHEDULE OF EVENTS TABLE

Schedule of Events Timepoint/Visit	Screen	Baseline	ARM 1 - PreDischarge from SSU	ARM 2 - PreDischarge from Hospital Floor	30-Day & 90 Day Follow up
Informed Consent	X				
Medical History		X			
Physical Exam		X	X	X	
Clinical lab tests*		X	X~	X~	
ECG*		X			
CXR*		X			
KCCQ (QoL) & SF-12			X	X	X
Oberst Caregiving Burden Scale and Bakas Caregiving Outcomes Scale			X	X	X ¹
HF Guideline Assessment			X	X	
Collect concomitant meds		X	X	X	
mRUQ-HF (resource utilization)					X ²
Cost Effectiveness Measures (i.e. DRG)					X
Guideline adherence assessment		X	X	X	X ¹
SCPC Discharge Criteria Adherence			X	X	
Assessment of AE/SAE's through 5 days			X	X	
Vital Status, ED visits, Hospital days, Re-admission status			X	X	X
Subject Payment			X	X	X ²

*per standard of care. Typical labs include: Na, K, renal function, HgB, troponin, Natriuretic Peptide levels. ~only if performed per usual care

SOC = standard of care, ED = Emergency Department, QoL = quality of life, HF = heart failure, mRUQ = modified resource utilization questionnaire, EMR = electronic medical record, DRG = diagnosis related group

¹Only through 30 days

²Sites may choose to make a single payment or to divide into 2 payments.

³only at 90 days

NOTE: If patients are hospitalized from the SSU, ONLY the following assessments should be collected. Otherwise, the pre-discharge assessments will apply.

- Physical exam
- Clinical lab tests
- Con meds
- SCPC discharge criteria. This would be conducted twice. Once in SCPS prior to hospitalization and again at discharge.

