Adherence to guidelines saves lives and reduces hospitalizations and re-hospitalizations. We expect both the primary and secondary outcome will be affected by adherence to guidelines. Advances in medical therapy for HF patients with reduced ejection fraction (EF) prolongs life and decreases hospitalization.³⁹ Yet a substantial proportion of patients are

either not taking guideline-recommended medications or are on sub-optimal doses.^{63,64} We will emphasize and measure guideline adherence for eligible patients at the point of discharge from both study arms as well as during follow up.

Guideline adherence: the following HF measures will be assessed in **eligible** patients:^{47,65-67} (1) assessment of left ventricular function within a 12 month period, (2) use of angiotensin-converting enzyme inhibitor or angiotensin receptor blocker or ARNI (angiotensin receptor blocker/neprilysin inhibitor) for left ventricular systolic dysfunction (defined as an ejection fraction < 40%), (3) Use of guideline recommended Beta-blocker for left ventricular systolic dysfunction, (4) use of mineralocorticoid receptor antagonists (5) use of ivabradine (6) use of hydralazine/isosorbide dinitrate (7) provision of discharge instructions, (8) counseling for smoking cessation, and (9) follow up appointment provided within 7 days of discharge. A composite heart failure measure will be created by averaging all quality measures available per patient. Specifically, the *composite score* is defined as the total number of interventions performed divided by the total number of interventions for which the patient was eligible. In addition, we will assess for therapies prescribed inappropriately such as glitazones or ARNI prescribed simultaneously with an ARB.

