10.2 STATISTICAL HYPOTHESES

Aim 1: To demonstrate the effectiveness of a SSU AHF management strategy vs. usual AHF care (i.e. inpatient admission), using a randomized, controlled, simple trial design.

- **Hypothesis 1a:** SSU treated patients will have one more DAOOH within 30 days post-randomization vs. usual care arm. Assuming a 10% attrition rate, we will randomize 534 patients 1:1, which will provide 80% power (alpha 0.05, two-sided) to demonstrate a one-day difference in the primary outcome at 30 days post-randomization.
- **Hypothesis 1b:** An AHF SSU strategy of care will lead to significant improvement in QoL scores at 30 days post-discharge compared with usual care. QoL will be assessed with the KCCQ.⁵⁹

Aim 2: To demonstrate if a SSU AHF strategy of care leads to equivalent or improved adherence to HF guidelines at time of discharge compared to usual care.

- **Hypothesis 2:** Adherence to HF guidelines at time of discharge in the SSU arm is equivalent or better than adherence in the usual care arm.

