10.4 DESCRIPTION OF STATISTICAL METHODS

10.4.1 GENERAL APPROACH

Unless stated otherwise, two-sided p values < 0.05 will be considered statistically significant, without regard to multiple comparisons. Statistical tables and listings and analyses will be produced using SAS® release 9.1 or later (SAS Institute, Inc, Cary, NC, USA) or other validated statistical software.

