10.4.3.1 ADDITIONAL ANALYSES

Exploratory Analyses: As observation is not an admission, payers cover out of pocket costs differently.

Guideline Adherence: Adherence to HF guidelines at time of discharge in the SSU arm is equivalent or better than adherence in the usual care arm.

Sample Size Calculation: We assume that the adherence percentage is 85% in the control arm.⁶⁴ With 240 subjects in each arm, we will have 80% power to detect an absolute improvement of 8% in the SSU arm, where the type I error rate is controlled at 0.05 (two-sided). Adherence to HF-Guidelines will be assessed based on the established Get-With-The-Guidelines HF (GWTG-HF) metrics for eligible patients. These measures have been previously well established.^{64,74}

HF Guideline Adherence Analysis: Fisher's exact test will be used to compare the percentage of adherence. Please see below regarding sensitivity analysis and missing data approaches.

CB Scale: Sample size (both arms combined)	% of data attrition	Effect size in CB scale
480	10%	0.25
360	33%	0.30
240	55%	0.37
120	78%	0.51

Caregiver Burden Analysis: This will be similar to the KCCQ analysis. See table for sample size considerations.

Sub-group analysis: The nature of the sub-group analysis is exploratory and will be used to generate hypotheses for future testing. We will study four pre-specified sub-groups: 1) older patients, defined as greater than 75 years old; 2) gender; 3) race and 4) insurance status (Medicaid, self-pay, Medicare, Commercial). The rationale for selecting these sub-groups is based either on known cardiovascular disparities or there is limited data regarding an SSU strategy in these specific subgroups.⁴⁶ The hypothesis: there will be no differences in outcomes, QoL, or guideline adherence between any of these groups. If the primary endpoint is achieved, we aim to demonstrate the AHF SSU strategy is broadly applicable across all subgroups. If there are differences, however, this may either demonstrate areas in need of further study, or initial subgroups to target. To test these hypotheses, we will compare the treatment benefit between sub-groups by formal two-sample testing procedures using normal approximation (e.g. Z test). A permutation test will also be performed as a sensitivity analysis. Given the limited sample size and the exploratory nature of the sub-group analysis, no multiple comparison adjustment will be made for these tests.

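### Aim 2 seeks guideline adherence equivalent to or better than usual care, but the planned two-sided Fisher test, with no margin, can support only the better half

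*Combined protocol and SAP*

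**What the plan says.** Section 3 (Objective 2) aims to demonstrate that SSU care "leads to equivalent or improved adherence to HF guidelines at time of discharge vs. usual care". Section 10.2 turns this into Hypothesis 2: "Adherence to HF guidelines at time of discharge in the SSU arm is equivalent or better than adherence in the usual care arm". The Précis states the same aim, and Section 10.4.3.1 repeats the hypothesis.

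The analysis is in Section 10.4.3.1. Usual-care adherence is taken as 85%, and the power statement reads "With 240 subjects in each arm, we will have 80% power to detect an absolute improvement of 8% in the SSU arm", at a two-sided type I error of 0.05. Fisher's "exact test will be used to compare the percentage of adherence". Section 10.4.1 supplies the general criterion: "two-sided p values < 0.05 will be considered statistically significant".

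The outcome is defined in Section 10.1.1. Nine measures are assessed in eligible patients, and the composite score for each patient is "the total number of interventions performed divided by the total number of interventions for which the patient was eligible". Section 10.4.3.1 adds that adherence follows the GWTG-HF metrics.

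On timing, Section 10.1.1 plans measurement "at the point of discharge from both study arms as well as during follow up". The "Guideline adherence assessment" row of the Section 7.3.7 schedule covers baseline, pre-discharge and follow-up through 30 days. The Précis lists the endpoint at discharge and Section 4.2.3 lists it at 30 days. Both call it exploratory.

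**The concern.** The hypothesis has two halves and the test addresses one. A two-sided test of no difference can show that SSU is better, or that it is worse. When it shows neither, it does not establish that the arms are close enough to call equivalent. That needs a stated largest acceptable deficit and a rule comparing a confidence bound with it. The documents give neither. The inverse probability weighting and subgroup tests in Section 10.4.3.1, and the multiple imputation in Section 10.4.5, do not supply one.

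The null result is also the expected result when the arms really are the same. The case that equivalent describes would therefore end in a p-value the plan cannot interpret, and a real deficit of several points would often look identical. In an open-label trial (Section 10.6.1), deciding after the data are seen what counts as equivalent, or which patients count as adherent, leaves the Aim 2 conclusion to choice.

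**Working it through.** **Inputs.** From Section 10.4.3.1: control 85%, SSU 93% under the planned effect, 240 per arm, two-sided 0.05, Fisher's exact test. From Section 10.5: 534 randomised (267 per arm), with 240 per arm left after 10% attrition. Assumption for steps 1 to 4: one binary outcome, evaluable in every counted patient.

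**1. The plan's own figure.** Pooled normal approximation, with mean proportion (0.85 + 0.93)/2 = 0.89:

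- SE under the null = √(2 × 0.89 × 0.11/240) = 0.02856
- SE under the alternative = √((0.85 × 0.15 + 0.93 × 0.07)/240) = 0.02833
- Power = Φ((0.08 − 1.960 × 0.02856)/0.02833) = 80.2%

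The stated 80% reproduces, as a superiority calculation by an uncorrected chi-square approximation. Exact enumeration over the two binomials gives the named Fisher test 76.8% at 240 per arm, 80.0% at 257 and 81.7% at 267. This is a side note, since more than 240 per arm may be evaluable at discharge.

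**2. How often the test is non-significant when SSU is not better.** Same enumeration, control 85%:

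| True SSU adherence | 240 per arm | 267 per arm |
|---|---|---|
| 85% (equal) | 96% | 96% |
| 80% (5 points worse) | 74% | 71% |
| 77% (8 points worse) | 43% | 38% |

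At 240 per arm the probability falls below one half between 7 points worse (54%) and 7.5 points worse (49%).

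**3. A possible result.** Usual care 204/240 (85.0%), SSU 188/240 (78.3%):

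- Difference = −6.7 points
- SE = √(0.85 × 0.15/240 + 0.783 × 0.217/240) = 0.0352
- 95% CI = −6.7 ± 1.96 × 3.52 = −13.6 to +0.2 points
- Fisher p = 0.076; chi-square p = 0.059

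The data are compatible with a 13-point deficit, the test is non-significant, and the plan does not say whether Hypothesis 2 is met.

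**4. What a margin would imply.** The documents give none, so these are illustrations. Power is the probability that the lower limit of the two-sided 95% CI for SSU minus usual care lies above minus the margin, with 85% in both arms:

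| Margin | 240 per arm | 267 per arm |
|---|---|---|
| 5 points | 34% | 37% |
| 8 points | 69% | 74% |
| 10 points | 87% | 90% |

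The margin giving 80% power is (1.960 + 0.842) × √(2 × 0.85 × 0.15/n), which is 9.1 points at n = 240 and 8.7 points at n = 267.

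For the composite as a continuous score, power = Φ(margin/(SD × √(2/240)) − 1.96). The documents give no SD. At a 5-point margin, assumed SDs of 0.15, 0.20, 0.25 and 0.35 give 95%, 78%, 59% and 35%.

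**5. Outcome against test.** Section 10.1.1 gives each patient a fraction between 0 and 1. Section 10.4.3.1 applies to a percentage a test that needs a two-by-two table. No text says what score makes a patient adherent, or whether the unit is the patient, the single measure or the eligible opportunity. As written, the test cannot be carried out without a further choice.

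**The case against.** The strongest reply is that Hypothesis 2 is a disjunction: a significant result favouring SSU would satisfy it, and the stated power for that is arithmetically sound. Both points are correct. What remains is the case where superiority is not shown, and there the plan has no rule.

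A second reply is that the endpoint is exploratory and the primary analysis is untouched. That limits the weight of the point but does not remove it, because adherence is the whole of one of two stated aims and has its own hypothesis and power statement.

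Third, Fisher's test is not the only analysis touching this subject. Section 10.4.2 compares discharge medications between arms, and Section 10.4.3.1 includes adherence in the subgroup tests. It is the only main comparison for Aim 2, and none of the others carries a margin.

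Fourth, a yes/no definition may lie in the GWTG-HF sources cited, or Fisher's test may be meant measure by measure among eligible patients. Either is possible, and the documents state neither. Under the second reading the numbers per arm would be below 240 for measures restricted to low ejection fraction, so the figures above would be optimistic.

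Finally, the timing difference is minor. Aim 2 and Hypothesis 2 both specify discharge, and only the Section 4.2.3 list says 30 days.

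**Conclusion.** The concern holds. The planned test can support better but cannot support equivalent, and the likeliest outcome under true equality is a result the plan cannot interpret. The percentages rest on the plan's 85% control rate and on a binary outcome evaluable in 240 or 267 per arm; the missing decision rule does not depend on them. The undefined binary outcome is a second gap in the same analysis. The power shortfall for Fisher's test (76.8% against 80%) and the endpoint-list timing are side notes. This should be corrected before analysis. It bears on the Aim 2 conclusion and not on DAOOH.

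**What to change.** 1. Pre-specify and justify a non-inferiority margin, and decide Hypothesis 2 by the lower limit of the two-sided 95% CI for SSU minus usual care. If it is met, test superiority. If no margin can be justified, remove equivalent from Aim 2 and Hypothesis 2 and report the difference with its 95% CI. For an exploratory endpoint that second route is a reasonable first choice.
2. Name one outcome and a matching analysis: either the Section 10.1.1 composite as a continuous score, in the arm-plus-site linear model that Section 10.4.2 plans for DAOOH, or a defined binary outcome with a risk difference.
3. State power for that analysis and the number expected to be evaluable at discharge.
4. In the endpoint lists, give the discharge assessment as the one that tests Hypothesis 2 and the 30-day assessment as a separate time point.

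**Cost.** No extra patients or data are needed to adopt the rule, but the sponsor must justify a margin and accept the power it brings. With a binary outcome and the present sample size, a margin much tighter than 9 points falls short of 80%; a 5-point margin would need (1.960 + 0.842)² × 2 × 0.85 × 0.15/0.05² = 801 per arm. The composite may do better, depending on an SD the documents do not give.

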10.5 SAMPLE SIZE

A one-day difference in the length of hospital stay is a 20% reduction in the mean length of stay(LOS) of five days during hospitalization (median LOS =4.3 days).⁵⁰ Pilot data support the clinical significance of a one-day reduction,⁴⁵ and discussions with patients and caregivers confirms this finding. *While we anticipate achieving greater than a one-day difference, we have powered our study conservatively.*

$$N (\text{total}) = 534; \quad N_1 = 267; \quad N_2 = 267$$

Based on published data,⁴⁶ we project that DAOOH has a mean of 25.6 with a standard deviation of 3.9 in the control arm. A reduction of the mean DAOOH by one-day is the minimal clinically meaningful difference as determined through our patient engagement outreach.⁵⁴ An interim analysis when half of the outcome data are available will be performed. (See DSMB, section E6). Accounting for this with the O'Brien-Fleming spending function, 240 subjects per arm are required to achieve 80% power in detecting the one-day difference in DAOOH, where the two-sided type I error rate is controlled at 0.05. Assuming 10% attrition due to drop-outs and lost to follow up, this study requires a total of 534 subjects. This power calculation also takes into account a conservative estimate of 40% of patients being admitted to the hospital from the SSU arm. *DAOOH automatically accounts for death.* The maximal number of days alive and out of the hospital through 30 days post randomization is 30 days. If a patient were to die on day 8 post-randomization, her DAOOH would be 8. This would be compared to a patient who stayed in the hospital 3 days after randomization, but never returned to the ED or hospital or died through 30 days. DAOOH of this patient would be 27. If the same patient returned to the hospital on day 12 for 2 days, and again on day 24 for 2 days, their total DAOOH would be 23.

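### The exploratory subgroup paragraph aims to demonstrate broad applicability using only tests of difference, which cannot show that benefit is similar

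*Combined protocol and SAP*

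**What the plan says.** The sub-group paragraph in section 10.4.3.1 pre-specifies four factors: age over 75, gender, race and insurance status (four categories). It presents the analysis as exploratory and meant to generate hypotheses. It then makes three statements:

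- The hypothesis is the null: "The hypothesis: there will be no differences in outcomes, QoL, or guideline adherence between any of these groups".
- The aim, conditional on success for the primary endpoint: "we aim to demonstrate the AHF SSU strategy is broadly applicable across all subgroups".
- The tool: "we will compare the treatment benefit between sub-groups by formal two-sample testing procedures using normal approximation (e.g. Z test"), with a permutation test as a sensitivity analysis.

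The paragraph mentions the limited sample only as a reason for making no multiplicity adjustment. The default threshold is in section 10.4.1: "two-sided p values < 0.05 will be considered statistically significant, without regard to multiple comparisons". The documents give no similarity margin, no confidence-interval criterion, no power for the subgroup comparisons and no expected subgroup sizes.

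**The concern.** A test of difference can give evidence against equal benefit. It cannot give evidence for it unless the precision is shown to be enough to exclude differences that matter. Here the hypothesis is the null, the aim is a positive statement about all subgroups, and nothing links the two except tests of difference. The paragraph goes on to say what detected differences might mean, so a reader will naturally take the absence of significance as support for applicability.

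The factors were chosen because of known disparities or sparse data on SSU care. If the trial succeeds overall, these are the groups for which an applicability statement would be used, and the smaller ones are where the data would say least.

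**Working it through.** **Inputs.** All but the allocation come from section 10.5. The SD: "we project that DAOOH has a mean of 25.6 with a standard deviation of 3.9 in the control arm". The evaluable number and target effect: "240 subjects per arm are required to achieve 80% power in detecting the one-day difference in DAOOH". Alpha is 5%, two-sided, and allowing for 10% loss brings the total to 534. Allocation is 1:1 (section 10.6.1). I assume the same SD in both arms and all subgroups, and 1:1 allocation within each subgroup. Subgroup shares are my assumption.

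**The plan's own figure.** Per arm, n = 2 × [3.9 × (1.960 + 0.842) / 1]² ≈ 239. The t-test version gives 239.7, and an assumed O'Brien-Fleming inflation of about 1.008 gives about 241, against 240 stated. Power at 240 per arm is 80.2%, and 480 / 0.9 rounds up to 534. The stated sample size reproduces.

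**Difference in benefit between two subgroups.** With N = 480 evaluable and smaller-subgroup share s:

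SE = 3.9 × √[4/(N·s) + 4/(N·(1−s))]

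At s = 0.5: 3.9 × √(4/240 + 4/240) = 0.712 days. This is twice the SE of the overall effect, 3.9 × √(2/240) = 0.356.

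Miss rate for a true difference d = 1 − [Φ(d/SE − 1.96) + Φ(−d/SE − 1.96)]. The difference detectable with 80% power is 2.80 × SE, and the 95% CI half-width is 1.96 × SE.

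| Share s | SE (days) | Miss rate, d = 1 day | Detectable, 80% power (days) | CI half-width (days) |
|---|---|---|---|---|
| 50% | 0.712 | 71.0% | 1.99 | 1.40 |
| 40% | 0.727 | 72.0% | 2.04 | 1.42 |
| 30% | 0.777 | 74.9% | 2.18 | 1.52 |
| 25% | 0.822 | 77.1% | 2.30 | 1.61 |
| 20% | 0.890 | 79.8% | 2.49 | 1.74 |
| 10% | 1.187 | 86.6% | 3.32 | 2.33 |

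If all 534 were evaluable, the miss rate would be 68.4% at 50:50 and 78.0% at 20:80. For pairwise contrasts of insurance categories, with assumed category sizes between 48 and 240, it is about 81-90%. About 1,910 evaluable patients would be needed for 80% power on a one-day interaction at 50:50.

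**One subgroup gains nothing and the overall effect is the planned one day.** The other subgroup must then gain 1/(1−s) days, which is also the difference in benefit d:

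| Share gaining nothing | d (days) | Miss rate |
|---|---|---|
| 50% | 2.00 | 20% |
| 40% | 1.67 | 37% |
| 35% | 1.54 | 46% |
| 30% | 1.43 | 55% |
| 25% | 1.33 | 63% |
| 20% | 1.25 | 71% |

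For example, at 30%: 1.43/0.777 = 1.84, and Φ(1.84 − 1.96) ≈ 0.45, so about 55% are missed.

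These figures cover DAOOH only. I give none for the other two outcomes named in the hypothesis. The KCCQ standard deviation in section 10.4.3 is for one-week change, not 30 days. Adherence is a per-patient composite limited to eligible measures in section 10.1.1, but is powered as a simple percentage in section 10.4.3.1.

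**The case against.** The paragraph carries its own caveats. It is labelled exploratory, it acknowledges the small sample, the factors are pre-specified, and it compares benefit between subgroups, which is the right contrast. The aim applies only if the primary endpoint is met. All of this stands, and it keeps the point outside the confirmatory analysis. It does not remove the tension, because an analysis meant to generate hypotheses cannot also demonstrate applicability. The sample-size caveat is used only to justify unadjusted testing. It is not used to warn that a null result says little.

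A reader might infer that the plan makes p > 0.05 its criterion for similarity. No sentence says that. It is the natural reading only because no other criterion is offered.

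A reader might also infer from the 71-80% that a subgroup with no benefit would usually go unnoticed. The documents do not support that in general. At 50:50, gains of zero and one day average to half a day overall, where the primary test has only 29% power, so the condition for the applicability aim would usually not be met. With the overall effect held at one day, the miss rate is 20% at a 50% share and passes one half only at a share of about 30% or below. The plan also expects an overall effect above one day, which would lower these rates further.

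Finally, the shares are assumed, so no single range describes every planned test.

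**Conclusion.** The point holds as a wording and reporting defect in an exploratory paragraph. The stated aim is one that the named tests cannot deliver. On the plan's SD and evaluable sample, for assumed two-level splits from 50:50 to 20:80, a one-day difference in benefit is missed about 71-80% of the time. Only differences of about 2.0-2.5 days, at least about twice the overall target, are detectable with 80% power. With a half-width of 1.4-1.7 days, even an observed difference of exactly zero would leave a one-day difference in either direction inside the interval, and section 10.5 treats one day as the smallest meaningful effect.

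The risk is greatest for small subgroups: where one gains nothing and the overall effect is one day, the miss rate is about 55% at a 30% share and 71% at 20%. The results rest on a common SD of 3.9, 480 evaluable patients and the assumed shares. Nothing here touches the validity of the primary or secondary analyses or the sample size.

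**What to change.** In section 10.4.3.1:

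- Remove the no-difference hypothesis and the aim to demonstrate broad applicability. Keep the exploratory label.
- Report the SSU effect with a 95% CI in each subgroup, and the difference in effect (interaction) with a 95% CI for each factor.
- State the approximate detectable interaction for DAOOH, about 2.0-2.5 days with 80% power, together with the assumed splits. Replace these with the observed subgroup shares when reporting.
- State that a non-significant interaction is not evidence of similar benefit.

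I would not add a formal similarity margin. Using the one-day overall difference as an interaction margin is debatable, and the expected intervals are too wide to fit inside it.

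The cost is SAP wording and a subgroup table or forest plot, with no extra patients or data. The downside is a less favourable applicability statement.

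### The subgroup plan aims to demonstrate broad applicability, but its only route there is a non-significant difference test, which cannot support that conclusion

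*Combined protocol and SAP*

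**What the plan says.** The sub-group paragraph of section 10.4.3.1 pre-specifies four factors: age above 75 years, gender, race, and insurance status in four categories (Medicaid, self-pay, Medicare, commercial). It opens by calling the analysis exploratory and a source of hypotheses for later testing. It closes by citing the limited sample size and the exploratory purpose as reasons for not adjusting for multiplicity.

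Between those two statements it sets a hypothesis: "The hypothesis: there will be no differences in outcomes, QoL, or guideline adherence between any of these groups". It then states an aim: "If the primary endpoint is achieved, we aim to demonstrate the AHF SSU strategy is broadly applicable across all subgroups". Finding differences is treated as the alternative case, which would point to further study or to subgroups to target first.

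On method: "we will compare the treatment benefit between sub-groups by formal two-sample testing procedures using normal approximation (e.g. Z test", with a permutation test as a sensitivity analysis. The default criterion comes from section 10.4.1: "two-sided p values < 0.05 will be considered statistically significant, without regard to multiple comparisons". The paragraph gives no equivalence margin, no confidence-interval rule and no power for the interaction tests.

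**The concern.** A hypothesis of no difference, tested only for difference, can be rejected or not rejected. It cannot be shown to be true. The plan nevertheless attaches a positive conclusion to the absence of differences, and it provides no tool that could establish that conclusion.

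At stake is what the report may claim. If the primary endpoint is met, the most likely subgroup finding is that no interaction reaches p < 0.05, whether or not the benefit is shared. The aim as written invites that finding to be reported as support for use in every group. Section 10.4.3.1 says the subgroups were chosen because of known disparities or limited data, so false reassurance would matter in just these groups.

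There is a smaller, separate problem. A two-sample test compares two groups, and insurance status has four. The plan does not say how four levels are to be compared.

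**Working it through.** **Inputs from the documents (sections 10.4.1, 10.5 and 10.6.1).** Two-sided alpha 0.05; 1:1 allocation. On the SD: "we project that DAOOH has a mean of 25.6 with a standard deviation of 3.9 in the control arm". On the effect: "A reduction of the mean DAOOH by one-day is the minimal clinically meaningful difference". On size: "240 subjects per arm are required to achieve 80% power in detecting the one-day difference in DAOOH", and "Assuming 10% attrition due to drop-outs and lost to follow up, this study requires a total of 534 subjects".

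**Assumptions not in the documents.** The smaller subgroup holds a share f of 50%, 30% or 20%. The SD is 3.9 in both arms and all subgroups. Allocation is 1:1 within subgroups.

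**1. The plan's own figure.** Fixed design: n per arm = 2 × (1.960 + 0.842)² × 3.9² / 1² = 238.8, so 239. With one look at half the information and O'Brien-Fleming-type spending (critical values 2.963 and 1.969), 240 per arm gives 80.06% power. 480 / 0.90 = 533.3, so 534. The sample size reproduces.

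**2. Standard error of the interaction**, N = 480:

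SE = 3.9 × √[4/(N f) + 4/(N(1 − f))]

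- f = 50%: 3.9 × √(4/240 + 4/240) = 0.712
- f = 30%: 3.9 × √(4/144 + 4/336) = 0.777
- f = 20%: 3.9 × √(4/96 + 4/384) = 0.890

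**3. Power for a one-day interaction and CI width.** Power = Φ(1/SE − 1.96) + Φ(−1/SE − 1.96); half-width = 1.96 × SE.

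| Smaller share | Power, 1 day | 95% CI half-width | Interaction detectable with 80% power |
|---|---|---|---|
| 50% | 29.0% | 1.40 days | 1.99 days |
| 30% | 25.1% | 1.52 days | 2.18 days |
| 20% | 20.2% | 1.74 days | 2.49 days |

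Even an estimated interaction of exactly zero would leave a one-day difference inside the interval. At a 10% share, power is 13.4%. If all 534 were evaluable, it would be 31.6% at a 50% share and 22.0% at 20%.

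**4. A subgroup with no benefit when the overall effect is as planned.** The sentence on applicability is conditional on the primary endpoint being met, so the relevant case keeps the overall effect at one day. If a share f gains nothing, the rest must gain 1/(1 − f) days, and that is the interaction.

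| Share with zero benefit | Interaction | Power | Not significant |
|---|---|---|---|
| 50% | 2.00 days | Φ(2.00/0.712 − 1.96) = 80% | 20% |
| 30% | 1.43 days | Φ(1.43/0.777 − 1.96) = 45% | 55% |
| 20% | 1.25 days | Φ(1.25/0.890 − 1.96) = 29% | 71% |

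The overall and interaction estimates are uncorrelated in this set-up. The chance that the primary is met and the interaction is also non-significant is therefore about 0.80 times the last column: 16%, 44% and 57%.

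**5. Insurance status.** Four levels give 4 × 3 / 2 = 6 possible pairs. If two levels each hold 25% of patients (assumed), SE = 3.9 × √(4/120 + 4/120) = 1.007, and power for a one-day interaction is about 17%.

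**The case against.** The strongest reply is that the plan never says a non-significant test shows applicability. The sentence is an aspiration, and the no-difference statement can be read as the null hypothesis of an ordinary interaction test. The paragraph calls itself exploratory, admits the limited sample and claims no power for subgroups. It also compares treatment benefit between subgroups, which is the right kind of comparison. Low interaction power is usual in any trial sized at 80% for its main effect.

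Most of this stands. A reader might infer that the plan contains a rule equating non-significance with applicability; it does not. What remains is narrower: with this hypothesis, these tests and no margin, the plan offers no other route to the conclusion it aims for. The exploratory label conflicts with an aim to demonstrate something and does not cure it. A small sample makes a conclusion from null findings weaker still.

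A reader might also infer from 20–29% power that a subgroup with no benefit would be missed in 71–80% of trials. That holds only if the other subgroup gains exactly one day. The overall effect would then be 0.5, 0.7 or 0.8 day at shares of 50%, 30% and 20%, with primary power (fixed design) of only about 29%, 50% and 61%, whereas the sentence applies only when the primary is met. The figures in step 4 of the working are the relevant ones.

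On insurance, the Z test is given only as an example and six pairwise tests are planned nowhere. The point is a missing specification.

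**Conclusion.** The point holds as a matter of permitted interpretation in an exploratory section. Non-significant subgroup tests in this trial cannot support broad applicability. Power for an interaction as large as the whole planned effect is about 20–29%, and the interval for the interaction extends 1.4 to 1.7 days either side of the estimate, against a one-day minimal important difference. With the overall effect at one day, a subgroup with no benefit would pass unnoticed in about 20% of trials if it is half the patients, 55% if it is 30%, and 71% if it is 20%. The concern is therefore mainly about the smaller subgroups.

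These figures rest on assumed shares, a common SD of 3.9 and 480 evaluable patients. They cover DAOOH only; quality of life and guideline adherence, which the hypothesis also names, were not calculated. The primary analysis and the sample size are untouched, so this is a minor but worthwhile correction.

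**What to change.** In section 10.4.3.1:

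- Report the treatment effect in each subgroup and the arm-by-subgroup interaction, each with a 95% CI. Adjusting for site is optional.
- For insurance status, use one joint interaction test on 3 degrees of freedom in place of two-sample tests.
- Replace the sentence on demonstrating applicability with a statement that the analysis describes consistency of effect, and that non-significant interactions will not be read as evidence of equal benefit.

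If the investigators want to keep a positive claim of consistency, they would need to pre-specify a margin. With 480 patients the intervals would rarely be narrow enough to exclude a one-day difference: 80% power for a one-day interaction would need about 4 × 3.9² × 7.849 / (f(1 − f)) evaluable patients, which is 1,910 at an even split and 2,985 at 20/80.

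The cost is a text edit to the analysis plan and a weaker permitted claim about applicability. No extra data are needed.
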